10.12. Appendix 12: CRS and ICANS Grading, Mitigation

10.12.1. Cytokine release syndrome

CRS is a non-antigen-specific cytokine-associated toxicity that occurs as a result of high-level immune activation. CRS is a potentially life-threatening toxicity that has been observed following administration of immune-base therapies for cancer (antibodies and adoptive T-cell therapies). CRS is likely to be a common toxicity that can be managed through supportive care and anti-cytokine interventions.

In cases of suspected CRS, a serum sample should be provided for cytokine release assay analysis by the local lab as long as the sampling does not interfere with the medical treatment of the participant. If CRS is suspected, additional blood samples should also be collected for central cytokine analysis if not already scheduled.

Early intervention should be undertaken at the first sign of CRS; signs may include pyrexia, tachycardia, tachypnea and/or hypotension, and are temporally related to elranatamab in the absence of alternative etiologies.

CRS grading will follow ASTCT criteria (Lee et al, 2019)(Table 4). For CRS management, published treatment guidelines are recommended but they may be modified as needed by the responsible investigator according to the best practices at their institute (Neelapu et al, 2018; Neelapu, 2019).

Table 4. ASTCT CRS Grading

CRS parameter:	Fever ^a	With Hypotension	And/or ^b Hypoxia
Grade 1	Temp $\geq 38^{\circ}\text{C}$	None	None
Grade 2		Not requiring vasopressors	Requiring low-flow ^c nasal cannula, low-flow ^c facemask or blow-by
Grade 3		Requiring a vasopressor with or without vasopressin	Requiring high-flow ^c nasal cannula, high-flow ^c facemask, nonrebreather mask, or Venturi mask
Grade 4		Requiring multiple vasopressors (excluding vasopressin)	Requiring positive pressure (eg, CPAP, BiPAP, intubation and mechanical ventilation)

Note: Organ toxicities associated with CRS should be graded according to CTCAE v5.0 and do not influence CRS grading.

- a Fever: Temp $\geq 38^{\circ}\text{C}$ and not attributable to any other cause. In participants who have CRS then receive antipyretic or anti-cytokine therapy such as tocilizumab or steroids, fever is no longer required to grade subsequent CRS severity. In this case, CRS grading is driven by hypotension and/or hypoxia.
- b CRS grade is determined by the more severe event: hypotension or hypoxia not attributable to any other cause. For example, a participant with Temp of 39.5°C , hypotension requiring 1 vasopressor, and hypoxia requiring low-flow nasal cannula is classified as Grade 3 CRS.
- c Low-flow nasal cannula or facemask is defined as oxygen delivered at ≤ 6 L/min. Low flow also includes blow-by oxygen delivery, sometimes used in pediatrics. High-flow nasal cannula or facemask is defined as oxygen delivered at >6 L/min. This is modified from original ASTCT criteria to differentiate between low-flow and high-flow facemask.

Source: (Lee et al, 2019)

10.12.1.1. CRS management guidelines by ASTCT Severity Grading

(Neelapu et al, 2018; Neelapu, 2019)

For all participants during hospitalization for study intervention:

Monitor vital signs every 4 hours, minimally, for worsening of condition. Fever, regardless of grade of CRS, is managed as described under Grade 1 CRS.

Grade 1 CRS:

Fever

- Acetaminophen/paracetamol and hypothermia blanket for the treatment of fever.
- NSAIDs such as ibuprofen can be used as second treatment option for fever if not contraindicated.
- Assess for infection using blood and urine cultures, and chest radiography.
- Empiric broad-spectrum antibiotics and filgrastim if neutropenic.
- Maintenance IV fluids for hydration.
- Symptomatic management of constitutional symptoms or organ toxicity.
- Consider tocilizumab 8 mg/kg (maximum dose 800 mg) IV or siltuximab 11 mg/kg IV for persistent (lasting >3 days) and refractory fever.

Grade 2 CRS:

- Monitor vital signs every 4 hours, minimally, for worsening of condition.

Hypotension

- IV fluid bolus of 500-1000 mL of normal saline. Consider giving a second fluid bolus if systolic BP remains <90 mmHg.
- Consider tocilizumab 8 mg/kg (maximum dose 800 mg) IV or siltuximab 11 mg/kg IV for treatment of hypotension refractory to fluid boluses; tocilizumab can be repeated after 6 hours if needed.
- If hypotension persists after 2 fluid boluses and anti-IL-6 therapy, start vasopressors, consider transfer to ICU, obtain ECHO, and initiate other methods of hemodynamic monitoring.
- In participants at high-risk (bulky disease, older age and/or comorbidities) or if hypotension persists after 1-2 doses of anti-IL-6 therapy, dexamethasone can be used at 10 mg IV every 6 hours.

Hypoxia

- Supplemental oxygen.
- Tocilizumab or siltuximab ± corticosteroids and supportive care, as indicated for hypotension.

Grade 3 CRS:

- Monitor participant (including continuous ECG monitoring) in an ICU and obtain ECHO if not done already.

Hypotension

- IV boluses, as needed, as recommended for Grade 2 CRS.
- Tocilizumab and siltuximab as recommended for Grade 2 CRS if not administered previously.
- Vasopressors as needed.
- Dexamethasone 10 mg IV every 6 hours; if refractory, increase to 20 mg IV every 6 hours.

Hypoxia

- Supplemental oxygen including high-flow oxygen delivery.
- Tocilizumab or siltuximab plus corticosteroids and supportive care, as described above for Grade 2 CRS.

Grade 4 CRS:

- Monitor participant (including continuous ECG monitoring) in an ICU and obtain ECHO if not done already.

Hypotension

- IV boluses, anti-IL-6 therapy, vasopressors, and hemodynamic monitoring as recommended for Grade 3 CRS.
- Methylprednisolone 1 g/day IV.

Hypoxia

- Supplemental oxygen via positive pressure/mechanical ventilation.
- Tocilizumab or siltuximab plus corticosteroids and supportive care, as described above for Grade 2 CRS.

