10.12.2.1. ICANS Management Guidelines Per ASTCT

(Neelapu et al, 2018; Neelapu, 2019)

ICANS Grade 1:

- Vigilant supportive care; aspiration precautions; IV hydration.
- Withhold oral intake of food, medicines, and fluids; assess swallowing.
- Convert all oral medications and/or nutrition to IV if swallowing is impaired.
- Avoid medications that cause CNS depression.
- Neurology consultation.
- If suspected, evaluate for elevated ICP with fundoscopic exam for papilledema and lumbar puncture for CSF opening pressure.
- MRI of the brain with and without contrast; CT scan of the brain can be performed if MRI is not feasible.
- Daily 30 min EEG until symptoms resolve.
- Consider anti-IL-6 therapy with tocilizumab 8 mg/kg (maximum 800 mg) IV or siltuximab 11 mg/kg IV in case of concurrent CRS.

ICANS Grade 2:

- Supportive care and neurological work-up as described for Grade 1 ICANS.
- Anti-IL-6 therapy if associated with concurrent CRS, as described for Grade 1 ICANS and if not administered previously.
- Dexamethasone 10 mg IV every 6 hours or methylprednisolone 1 mg/kg IV every 12 hours if refractory to anti-IL-6 therapy, or for ICANS without concurrent CRS.

- Consider transferring participant to ICU if ICANS associated with Grade ≥ 2 CRS.

ICANS Grade 3:

- Supportive care and neurological work-up as indicated for Grade 1 ICANS.
- ICU transfer is recommended.
- If EEG shows non-convulsive status epilepticus:
 - Assess airway, breathing, and circulation; check blood glucose.
 - Lorazepam 0.5 mg IV, with additional 0.5 mg IV every 5 min, as needed, up to a total of 2 mg to control electrographical seizures.
 - Levetiracetam 500 mg IV bolus, as well as maintenance doses.
 - If seizures persist, transfer to ICU and treat with phenobarbital loading dose of 60 mg IV.
 - Recommended maintenance therapy after resolution of non-convulsive status epilepticus are as follows:
 - lorazepam 0.5 mg IV every 8 hours for 3 doses;
 - levetiracetam 1000 mg IV every 12 hours; duration of therapy per investigator/treating physician's discretion;
 - phenobarbital 30 mg IV every 12 hours; duration of therapy per investigator/treating physician's discretion.
 - Lacosamide may also be considered for treatment of seizures should the seizures persist. Lacosamide should not be used in participants with concurrent CRS in order to avoid arrhythmias and hypotension.
- For convulsive status epilepticus:
 - Assess airway, breathing, and circulation; check blood glucose.

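### The Grade 3 CRS hypotension line joins tocilizumab and siltuximab with *and*, although the Grade 2 rule it cites offers them as alternatives

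*Protocol*

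**What the plan says.** Protocol Section 10.12.1.1 (Appendix 12) sets out CRS management by ASTCT grade, with separate hypotension and hypoxia guidance from Grade 2 upward. Under Grade 3 hypotension, the anti-IL-6 line is "Tocilizumab and siltuximab as recommended for Grade 2 CRS if not administered previously".

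The Grade 2 hypotension rule to which it points is "Consider tocilizumab 8 mg/kg (maximum dose 800 mg) IV or siltuximab 11 mg/kg IV for treatment of hypotension refractory to fluid boluses". That rule goes on to allow a repeat of tocilizumab, but not siltuximab, after 6 hours.

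Directly below the Grade 3 hypotension guidance, the Grade 3 hypoxia line refers to the same Grade 2 recommendation and words it as "Tocilizumab or siltuximab plus corticosteroids and supportive care, as described above for Grade 2 CRS". Grade 4 hypotension names neither drug and defers to Grade 3: "IV boluses, anti-IL-6 therapy, vasopressors, and hemodynamic monitoring as recommended for Grade 3 CRS".

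**The concern.** The Grade 3 hypotension line attributes to Grade 2 a recommendation that Grade 2 does not make. A clinician who follows the printed word would give both anti-IL-6 agents. One who follows the cross-reference would choose one.

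The two wordings can meet in the same participant. Footnote b to Table 4 in Section 10.12.1 gives a worked grading example: "hypotension requiring 1 vasopressor, and hypoxia requiring low-flow nasal cannula is classified as Grade 3 CRS". For that participant the hypotension line says *and*. The hypoxia line says *or*, whether one uses the Grade 2 entry (which matches low-flow oxygen) or the Grade 3 entry (which matches the overall grade).

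At stake is the clarity of bedside guidance for a toxicity that the protocol itself describes as potentially life-threatening. A literal reading would also carry into Grade 4 hypotension through its reference to Grade 3.

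**Working it through.** No arithmetic beyond counting applies, and the plan states no figure here to reproduce. The check is to list every line in Appendix 12 that names both drugs, note the word joining them, and note whether the line refers back to the Grade 2 choice.

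| Line | Text | Joined by | Refers back to Grade 2 choice |
|---|---|---|---|
| CRS Grade 1, fever | "Consider tocilizumab 8 mg/kg (maximum dose 800 mg) IV or siltuximab 11 mg/kg IV for persistent (lasting >3 days) and refractory fever" | or | no |
| CRS Grade 2, hypotension | the cited rule, quoted above | or | it is the rule |
| CRS Grade 2, hypoxia | "Tocilizumab or siltuximab ± corticosteroids and supportive care, as indicated for hypotension" | or | yes |
| CRS Grade 3, hypotension | the line at issue, quoted above | **and** | yes |
| CRS Grade 3, hypoxia | quoted above | or | yes |
| CRS Grade 4, hypoxia | same words as Grade 3 hypoxia | or | yes |
| ICANS Grade 1 (Section 10.12.2.1) | "Consider anti-IL-6 therapy with tocilizumab 8 mg/kg (maximum 800 mg) IV or siltuximab 11 mg/kg IV in case of concurrent CRS" | or | no |

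Counts:

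- Lines naming both drugs: 5 in CRS Grades 1 to 3, plus 1 in CRS Grade 4, plus 1 in ICANS = 7. Of these, 6 say *or* and 1 says *and*.
- Lines referring back to the Grade 2 choice: 4. Of these, 3 say *or* and 1 says *and*.

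Grade 4 hypotension and ICANS Grades 2 to 4 speak only of anti-IL-6 therapy as a class. Footnote a to Table 4 names tocilizumab alone. None of these enters the count.

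Could *and* be a deliberate escalation at Grade 3? The text points the other way:

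1. Grade 3 hypotension escalates by steps that are spelled out: ICU monitoring, vasopressors as needed, and dexamethasone 10 mg every 6 hours, raised to 20 mg if refractory. The anti-IL-6 line is not presented as a new step; it defers to Grade 2.
2. Grade 3 hypoxia, and the more severe Grade 4 hypoxia, both keep *or*. Two agents for Grade 3 hypotension alone would not fit that pattern.
3. Appendix 12 gives no order or interval for using both agents. Its only repeat instruction is the 6-hour one for tocilizumab.
4. ICANS Grades 2 and 3 apply the same not-previously-given condition to anti-IL-6 therapy as a class. With *or*, the Grade 3 CRS line matches that usage.

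**The case against.** Four points can be made for leaving the line alone.

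- **The line limits itself.** It defers to Grade 2, so it can be read as naming the two agents that Grade 2 makes available, to be used as Grade 2 directs. On that reading it is loose rather than contradictory, and the worked example gives the same *or* choice under both headings. This stands as a reason to keep the severity low. It also supports the proposed word, and a reader should not have to override the printed text to reach it.
- **The guidance is advisory.** Section 10.12.1 lets the responsible investigator modify it to local best practice, and the documents state no harm from giving both agents. This also stands and limits the consequence, but it does not make the sentence correct.
- **The intent may lie in the cited management publications.** Their wording is not available here, so what they say is unknown. The finding does not depend on it: the protocol line misstates the protocol's own rule.
- **The change might remove an option.** For a participant who received tocilizumab at Grade 2 and then worsened, the present wording can be read agent by agent, leaving siltuximab open; *or* could be read as excluding both once either has been given. This is weak. The ICANS entries already use the condition for the class, and both higher-grade hypoxia lines keep *or*. A planned second agent after failure of the first would need its own explicit step, which the present line does not provide.

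**Conclusion.** The concern holds. The Grade 3 hypotension line is wrong as written: it is the only one of seven lines to use *and*, and the only one of the four that refer back to Grade 2 to restate that choice incorrectly. Confidence is high, because the conclusion rests only on the wording and cross-references inside Appendix 12.

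Severity is minor. The practical effect arises only if the line is followed literally, and the cross-reference, the neighbouring lines and the investigator-discretion clause all reduce the chance of that. No sample size, operating characteristic, enrollment-hold threshold or analysis is affected.

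**What to change.** In Section 10.12.1.1, Grade 3 hypotension, replace *and* with *or* between the two drug names and leave the rest of the sentence unchanged. Grade 4 hypotension needs no edit, because it points to Grade 3 and will inherit the corrected wording.

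Whether the 6-hour tocilizumab repeat allowed at Grade 2 also applies at Grade 3 is a separate question for the medical lead and is not part of this change.

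The cost is one word, made with the next amendment. The change aligns the line with the rule it already cites and introduces no new treatment.

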10.12.2. Immune effector cell-associated neurotoxicity syndrome (ICANS)

Although less commonly seen than CRS, ICANS has been observed with some T-cell directed therapies and may manifest as aphasia, delirium, encephalopathy, lethargy, difficulty concentrating, agitation, tremor, seizures, and cerebral edema (Lee et al, 2019). If ICANS is observed in relation to elranatamab, the ASTCT criteria will be used for grading and

published guidelines are recommended for management (Neelapu et al, 2018; Lee et al, 2019; Neelapu, 2019). These treatment guidelines may be modified as needed by the responsible investigator according to the best practices at their institute.

Table 5. Immune Effector Cell-Associated Encephalopathy (ICE) Score

Category	Task	Points
Orientation	Orientation to year, month, city, hospital	4
Naming	Ability to name 3 objects	3
Following commands	Ability to follow simple commands	1
Writing	Ability to write a standard sentence	1
Attention	Ability to count backwards from 100 by 10	1

Table 6. ASTCT ICANS Grading

Neurotoxicity Domain	Grade 1	Grade 2	Grade 3	Grade 4
ICE score ^a	7-9	3-6	0-2	0 (unarousable and unable to perform ICE)
Depressed level of consciousness ^b	Awakens spontaneously	Awakens to voice	Awakens only to tactile stimulus	Unarousable or requires vigorous or repetitive tactile stimuli to arouse. Stupor or coma
Seizure	N/A	N/A	Any clinical seizure that resolves rapidly or non-convulsive seizures on EEG that resolve with intervention	Life-threatening prolonged seizure (>5 min); or repetitive clinical or electrical seizures without return to baseline in between
Motor findings ^c	N/A	N/A	N/A	Deep focal motor weakness such as hemiparesis or paraparesis
Elevated ICP/cerebral edema	N/A	N/A	Focal/local edema on neuroimaging ^d	Diffuse cerebral edema on neuroimaging; decerebrate or decorticate posturing; or cranial nerve VI (abducens nerve) palsy; or papilledema; or Cushing's triad

090177e19f0abbfaApproved On: 31-Oct-2023 20:35 (GMT)

Table 6. ASTCT ICANS Grading

Neurotoxicity Domain	Grade 1	Grade 2	Grade 3	Grade 4
----------------------	---------	---------	---------	---------

Note: ICANS grade is determined by the most severe event (ICE score, level of consciousness, seizure, motor findings, raised ICP/cerebral edema) not attributable to any other cause; for example, a participant with an ICE score of 3 who has a generalized seizure is classified as Grade 3 ICANS.

- a A participant with an ICE score of 0 may be classified as Grade 3 ICANS if awake with global aphasia, but a participant with an ICE score of 0 may be classified as Grade 4 ICANS if unarousable.
- b Depressed level of consciousness should be attributable to no other cause (eg, no sedating medication).
- c Tremors and myoclonus associated with immune effector cell therapies may be graded according to CTCAE v5.0; these symptoms do not influence ICANS grading.
- d Intracranial hemorrhage with or without associated edema is not considered a neurotoxicity feature and is excluded from ICANS grading. It should be graded according to CTCAE v5.0.

Source: (Lee et al, 2019)

10.12.2.1. ICANS Management Guidelines Per ASTCT

(Neelapu et al, 2018; Neelapu, 2019)

ICANS Grade 1:

- Vigilant supportive care; aspiration precautions; IV hydration.
- Withhold oral intake of food, medicines, and fluids; assess swallowing.
- Convert all oral medications and/or nutrition to IV if swallowing is impaired.
- Avoid medications that cause CNS depression.
- Neurology consultation.
- If suspected, evaluate for elevated ICP with fundoscopic exam for papilledema and lumbar puncture for CSF opening pressure.
- MRI of the brain with and without contrast; CT scan of the brain can be performed if MRI is not feasible.
- Daily 30 min EEG until symptoms resolve.
- Consider anti-IL-6 therapy with tocilizumab 8 mg/kg (maximum 800 mg) IV or siltuximab 11 mg/kg IV in case of concurrent CRS.

ICANS Grade 2:

- Supportive care and neurological work-up as described for Grade 1 ICANS.
- Anti-IL-6 therapy if associated with concurrent CRS, as described for Grade 1 ICANS and if not administered previously.
- Dexamethasone 10 mg IV every 6 hours or methylprednisolone 1 mg/kg IV every 12 hours if refractory to anti-IL-6 therapy, or for ICANS without concurrent CRS.

- Consider transferring participant to ICU if ICANS associated with Grade ≥ 2 CRS.

ICANS Grade 3:

- Supportive care and neurological work-up as indicated for Grade 1 ICANS.
- ICU transfer is recommended.
- If EEG shows non-convulsive status epilepticus:
 - Assess airway, breathing, and circulation; check blood glucose.
 - Lorazepam 0.5 mg IV, with additional 0.5 mg IV every 5 min, as needed, up to a total of 2 mg to control electrographical seizures.
 - Levetiracetam 500 mg IV bolus, as well as maintenance doses.
 - If seizures persist, transfer to ICU and treat with phenobarbital loading dose of 60 mg IV.
 - Recommended maintenance therapy after resolution of non-convulsive status epilepticus are as follows:
 - lorazepam 0.5 mg IV every 8 hours for 3 doses;
 - levetiracetam 1000 mg IV every 12 hours; duration of therapy per investigator/treating physician's discretion;
 - phenobarbital 30 mg IV every 12 hours; duration of therapy per investigator/treating physician's discretion.
 - Lacosamide may also be considered for treatment of seizures should the seizures persist. Lacosamide should not be used in participants with concurrent CRS in order to avoid arrhythmias and hypotension.
- For convulsive status epilepticus:
 - Assess airway, breathing, and circulation; check blood glucose.
 - Transfer to ICU.
 - Lorazepam 2 mg IV, with additional 2 mg IV to a total of 4 mg to control seizures.
 - Levetiracetam 500 mg IV bolus, as well as maintenance doses.
 - If seizures persist, add phenobarbital at a loading dose of 15 mg/kg IV.
 - Maintenance doses after resolution of convulsive status epilepticus:
 - lorazepam 0.5 mg IV every 8 hours for 3 doses;
 - levetiracetam 1000 mg IV every 12 hours; duration of therapy per investigator/treating physician's discretion;
 - phenobarbital 1-3 mg/kg IV every 12 hours; duration of therapy per investigator/treating physician's discretion.

- Lacosamide may also be considered for treatment of seizures should the seizures persist. Lacosamide should not be used in participants with concurrent CRS in order to avoid arrhythmias and hypotension.
- Continuous EEG monitoring should be performed if seizures are refractory to treatment.
- High-dose methylprednisolone IV 1 g/day for focal/local edema.
- Anti-IL-6 therapy if associated with concurrent CRS, as described for Grade 1 ICANS and if not administered previously.
- Corticosteroids as outlined for Grade 2 ICANS if symptoms worsen despite anti-IL-6 therapy, or for ICANS without concurrent CRS; continue corticosteroids until improvement to Grade 1 ICANS and then taper.

ICANS Grade 4:

- Supportive care and neurological work-up as outlined for Grade 1 ICANS.
- ICU monitoring; consider mechanical ventilation for airway protection.
- Anti-IL-6 therapy and repeat neuroimaging as described for Grade 3 ICANS.
- High-dose corticosteroids continued until improvement to Grade 1 ICANS and then taper; for example, methylprednisolone IV 1 g/day for 3 days, followed by rapid taper at 250 mg every 12 hours for 2 days, 125 mg every 12 hours for 2 days, and 60 mg every 12 hours for 2 days.
- For convulsive status epilepticus, treat as described for Grade 3 ICANS.
- MRI of the spine should be obtained for focal motor weakness.
- To manage elevated ICP:
 - Elevate head of the participant's bed to an angle of 30 degrees.
 - Hyperventilation to achieve target PaCO₂ of 28–30 mmHg, but maintained for no longer than 24 hours.
 - Hyperosmolar therapy with either mannitol (20 g/dL solution) or hypertonic saline (3% or 23.4%, as detailed below):
 - Mannitol: initial dose 0.5–1 g/kg; maintenance at 0.25–1 g/kg every 6 hours while monitoring metabolic profile and serum osmolality every 6 hours, and withhold mannitol if serum osmolality is ≥ 320 mOsm/kg, or the osmolality gap is ≥ 40 .
 - Hypertonic saline: initial 250 ml of 3% hypertonic saline; maintenance at 50-75 mL/hour while monitoring electrolytes every 4 h, and withhold infusion if serum Na levels reach ≥ 155 mEq/L.
 - For participants with imminent herniation: initial 30 ml of 23.4% hypertonic saline; repeat after 15 min, if needed.

- If patient has Ommaya reservoir, drain CSF to target opening pressure of <20 mmHg
- Consider neurosurgery consultation for ventriculoperitoneal shunt in participants with cerebral edema, and IV anesthetics for burst-suppression pattern on EEG.
- Metabolic profiling every 6 hours and daily CT scan of head, with adjustments in usage of the aforementioned medications to prevent rebound cerebral oedema, renal failure, electrolyte abnormalities, hypovolemia, and hypotension.

